6.5.4 Special Precautions

The IMP should be temporarily withheld or permanently withdrawn if the following abnormalities occur or re-occur, as relevant, and only 1 re-initiation is allowed if the IMP is temporarily withheld:

- For a neutrophil count $< 500/\text{mm}^3$ or platelet count $< 25,000/\text{mm}^3$ (Grade 4) or neutrophil count 500 to 999/mm³ (Grade 3) with fever or platelet count 25,000 to 49,999/mm³ (Grade 3) with bleeding, the IMP should be permanently withdrawn.

- For a Grade 3 decrease in neutrophil count without fever or Grade 3 decrease in platelet count without bleeding, temporarily hold the IMP and recheck the value within 24 hours of receipt. If the value is still Grade 3, permanently discontinue the IMP. For a decrease from normal to Grade 1, or Grade 1 to Grade 2, temporarily hold the IMP and recheck the value within 24 hours of receipt. Discontinue the IMP if the neutrophil or platelet count continues to decrease, and re-initiate the IMP if no downward trend is observed.
- For an increase in AST or ALT to $> 3X$ ULN or increase in bilirubin to $> 1.5X$ ULN (Grade 2 or higher), the IMP should be permanently withdrawn.
- For an increase in amylase or lipase to $> 5X$ ULN (Grade 4), the IMP should be permanently withdrawn.
 - For an increase in amylase or lipase to > 2 to $5X$ ULN (Grade 3), temporarily hold the IMP and recheck the value within 24 hours of receipt. If the value is still Grade 3, permanently discontinue the IMP. For any other increase from Baseline to another grade, temporarily hold the IMP and recheck the value within 24 hours of receipt. Discontinue the IMP if the value does not decrease, or re-initiate the IMP if a downward trend is observed.
- For an increase in serum creatinine to $> 3X$ from Baseline (Grade 3 or higher), the IMP should be permanently withdrawn.
 - For any other increase in serum creatinine $> 1.5X$ from Baseline, temporarily hold the IMP and recheck the value within 24 hours of receipt. Discontinue the IMP if the value does not decrease, or re-initiate the IMP if a downward trend is observed.
- For any other laboratory abnormality of Grade 4 severity, the IMP should be permanently withdrawn.
 - For any other laboratory increase/decrease (as relevant) from Baseline to a higher severity grade, temporarily hold the IMP and recheck the value within 24 hours of receipt. Discontinue the IMP if the value does not improve, or re-initiate the IMP if an improving trend is observed.

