Duplicate blood samples will be collected for selected safety laboratories to be processed by both the central laboratory and local laboratories. A detailed list of these tests is provided in the Laboratory Manual. The Investigator should review local laboratory results within 24 hours and should base decisions regarding retesting or IMP dose interruption or discontinuation on local laboratory results if local laboratory results are obtained prior to the central laboratory results and show an abnormality requiring action. The local laboratory reference range should be used to determine grade in this case. Only the central laboratory results will be automatically reported and used for analyses. If an action is taken to retest or adjust the IMP dose based on local laboratory results, the results should be entered in the eCRF (with date, time and result, and local reference range) on an unscheduled visit page to document why the decision was made.

Laboratory values corresponding to Common Terminology Criteria for AEs (CTCAE) Grades 1 to 4 are presented for selected laboratory parameters in [Table 3](#). For all other laboratory abnormalities, refer to the CTCAE, version 4.03 ([20](#)).

Table 3 CTCAE Grades for Relevant Laboratory Parameters

Laboratory Parameter	Grade 1	Grade 2	Grade 3	Grade 4
Neutrophil (/mm ³)	< LLN to 1,500	< 1,500 to 1,000	< 1,000 to 500	< 500
Platelets (/mm ³)	< LLN to 75,000	< 75,000 to 50,000	< 50,000 to 25,000	< 25,000
AST and ALT	< ULN to 3X ULN	> 3 to 5X ULN	> 5 to 20X ULN	> 20X ULN
Bilirubin	< ULN to 1.5X ULN	> 1.5 to 3X ULN	> 3 to 10X ULN	> 10X ULN
Amylase and lipase	< ULN to 1.5X ULN	> 1.5 to 2X ULN	> 2 to 5X ULN	> 5X ULN
Creatinine	> Baseline to ≤ 1.5X Baseline, or > ULN to 1.5X ULN	> 1.5 to 3X Baseline or > 1.5 to 3X ULN	> 3X Baseline, or > 3 to 6X ULN	> 6X ULN

ALT=alanine aminotransferase, AST=aspartate aminotransferase, CTCAE=Common Terminology Criteria for Adverse Events, LLN=lower limit of normal, ULN=upper limit of normal.

The reason for IMP withdrawal and the nature, duration, and results of any planned follow-up observations should be recorded in the appropriate section of the eCRF.

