Unique Identifier for SAP Version	Date of SAP Version	Authors	Changes from the Previous Version
Final 1.0	18 April 2017	PPD [REDACTED], PPD [REDACTED]	NA – first version

5 Purpose of the Statistical Analysis Plan

The purpose of this Statistical Analysis Plan (SAP) is to document technical and detailed specifications for analyses of data collected for protocol MS200527-0081 dated 02 September 2016 (version 3.0). The SAP is based upon Section 8 (Statistics) of the trial protocol and is prepared in compliance with International Council for Harmonisation E9.

The first version (version 1.0) of the SAP includes details for the primary and final statistical analyses, planned for the end of 12 weeks treatment and for the end of study, respectively.

Results of the analyses described in this SAP will be included in the Clinical Study Report (CSR). Additionally, the planned analyses identified in this SAP will be included in regulatory submissions or future manuscripts. Any post-hoc, or unplanned analyses performed to provide results for inclusion in the CSR but not identified in this prospective SAP will be clearly identified in the CSR.

The final clinical database cannot be locked until the final SAP has been approved and signed.

Another SAP document (MS200527-0081_IA_IDMC_SAP_v3.0 08 Feb2017) detailed specifications for the Independent Data Monitoring Committee (IDMC) and Interim analyses (IA).

6 Summary of Clinical Trial Features

Clinical Trial Protocol Number	MS200527-0081
Title	A Phase IIa Randomized, Double-Blind, Placebo-Controlled Trial to Evaluate the Efficacy and Safety of M2951 in Subjects with Rheumatoid Arthritis on Stable Methotrexate Therapy
Trial Phase	IIa
IND Number	122,963
FDA covered trial	No
EudraCT Number	2016-000064-42
Coordinating Investigator	PPD [REDACTED] PPD [REDACTED] [REDACTED] [REDACTED] Phone PPD [REDACTED] Fax PPD [REDACTED] PPD [REDACTED]
Sponsor	Merck KGaA Darmstadt, Germany Medical Responsible: PPD [REDACTED] [name] Telephone: PPD [REDACTED]
Trial centers/countries	Approximately 50 sites in 10 countries
Planned trial period (first subject in-last subject out)	July 2016 to March 2017
Trial Registry	Clinicaltrials.gov

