8.4 Final Analysis

The final analysis will occur only when the last subject completes all study parts (or discontinues study prematurely), the protocol violations are determined and the database is locked for the final analysis.

9 Changes to the Planned Analyses in the Clinical Trial Protocol

Computation of point estimates and CIs of differences from baseline in hsCRP and Disease Activity Score based on 28 joints and high-sensitivity C-Reactive Protein (DAS28-hsCRP)

Details were added to complete the planned analysis of hsCRP and DAS28-hsCRP.

In the SAP, it has been further specified that:

- the differences in mean changes between M2951+MTX and Placebo+MTX will be considered for hsCRP and DAS28-hsCRP, along with the 2-sided 80% CI for the difference
- the estimates and the CI limits will be derived using an Analysis of Covariance (ANCOVA) model with baseline as a covariate and treatment group as an independent variable
- Percent Change From Baseline (CFB) of hsCRP will be provided as summary statistics

Missing hsCRP and DAS28-hsCRP imputation

Missing hsCRP values and DAS28-hsCRP scores will be imputed for the primary and final analyses:

- Missing hsCRP values will be imputed using the same rule used for the analysis of the primary endpoint, ie, post-baseline Last Observation Carried Forward (LOCF)
- Missing components of DAS28-hsCRP will be imputed using the same rule as the primary endpoint, i.e., post-baseline Last Observation Carried Forward (LOCF)

Imputation of hsCRP and DAS28-hsCRP is not applicable for open-label extension (OLE) period, only for 12-week treatment period.

CCI

OLE PD endpoints

The Schedule of Assessments table in protocol specifies immunoglobulin and B cells and subtypes to be collected during the optional OLE period. A description of the analysis of these data is missing from the “Endpoints for Open-label Extension” section of the protocol. A separate analysis set has been added here in Section 10.2.

CTCAE Grades for Relevant Laboratory Parameters

The Grade 1 definitions for the laboratory parameters AST, ALT, bilirubin, amylase, lipase, and creatinine in Table 3 in the protocol were cited incorrectly. For these parameters, Grade 1 will be defined as in CTCAE, version 4.03. In fact, all laboratory abnormalities will be graded as specified in CTCAE, version 4.03; Table 3 of the protocol will not be used.

PK statistical presentation

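### The amylase/lipase hold in protocol section 6.5.4 still turns on a Table 3 Grade 1 limit that the SAP calls wrong and no longer uses

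*SAP*

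**What the plan says.** SAP section 9, under the item on CTCAE grades, reports an error in the protocol: "The Grade 1 definitions for the laboratory parameters AST, ALT, bilirubin, amylase, lipase, and creatinine in Table 3 in the protocol were cited incorrectly". Its remedy concerns the analysis: "all laboratory abnormalities will be graded as specified in CTCAE, version 4.03; Table 3 of the protocol will not be used". The SAP does not print the limits it will use instead.

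The SAP is written for protocol version 3.0 of 02 September 2016, and that version still contains the table. Section 6.5.4 introduces it with "Laboratory values corresponding to Common Terminology Criteria for AEs (CTCAE) Grades 1 to 4 are presented for selected laboratory parameters in" Table 3, and sends the reader to CTCAE version 4.03 for all other abnormalities. Grade 1 for bilirubin and for amylase and lipase is printed as "< ULN to 1.5X ULN". The AST and ALT entry has the same form, with 3 times ULN as its upper end.

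The same section attaches actions to grades. After its explicit amylase and lipase limits it adds: "For any other increase from Baseline to another grade, temporarily hold the IMP and recheck the value within 24 hours of receipt". A final catch-all reads: "For any other laboratory increase/decrease (as relevant) from Baseline to a higher severity grade, temporarily hold the IMP". Where a local result arrives before the central one and shows an abnormality requiring action, the investigator decides on the local result: "The local laboratory reference range should be used to determine grade in this case".

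**The concern.** The SAP corrects the grading that will be reported. Nothing in the two documents corrects the grading that sites are told to act on. As printed, Grade 1 for the enzymes and bilirubin starts below ULN, so a normal value is already Grade 1. A rule triggered by moving to another grade then cannot be triggered by leaving the normal range.

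The stakes are modest but real. A hold under section 6.5.4 leads to a recheck, then to discontinuation if an amylase or lipase value does not fall, and only one re-initiation is allowed. Two readings of the Grade 1 limit can therefore produce different dosing histories for the same laboratory value. The SAP tabulates worst-grade shifts (section 17.3) and adverse events leading to interruption or withdrawal of study drug (section 17.1.1). It also counts failure to withdraw a subject who meets withdrawal criteria as an important deviation (section 10.1). A reader of those outputs needs to know which grading governed the action.

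**Working it through.** The plan states no figure on this point to reproduce. The check is to grade the same baseline-to-visit pairs under two readings of Grade 1 and see whether any action in section 6.5.4 changes.

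**Inputs.** The upper ends of Grades 1, 2 and 3 come from Table 3, in multiples of ULN: amylase/lipase 1.5, 2, 5; AST/ALT 3, 5, 20; bilirubin 1.5, 3, 10. Reading A takes Grade 1 as printed, so values below ULN are included. Reading B starts Grade 1 above ULN. Reading B is an assumption made only to show sensitivity; it is not proposed as the limit.

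**Rule.** A grade-change hold is triggered when the visit grade exceeds the baseline grade.

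| Parameter | Baseline to visit (x ULN) | Reading A | Reading B | Action differs? |
|---|---|---|---|---|
| Amylase/lipase | 0.8 to 1.0 | 1 to 1 | normal to normal | No; no hold on either |
| Amylase/lipase | 0.8 to 1.3 | 1 to 1 | normal to 1 | **Yes**; no hold under A, hold under B |
| Amylase/lipase | 0.8 to 1.6 | 1 to 2 | normal to 2 | No; hold on both |
| Amylase/lipase | 1.2 to 1.6 | 1 to 2 | 1 to 2 | No; hold on both |
| Amylase/lipase | 0.8 to 2.5 | 1 to 3 | normal to 3 | No; explicit rule for above 2 to 5 x ULN |
| Amylase/lipase | 0.8 to 6 | 1 to 4 | normal to 4 | No; explicit rule above 5 x ULN |
| AST/ALT | 0.8 to 2.0 | 1 to 1 | normal to 1 | Only if the catch-all applies |
| AST/ALT | 0.8 to 3.2 | 1 to 2 | normal to 2 | No; explicit withdrawal rule |
| Bilirubin | 0.8 to 1.3 | 1 to 1 | normal to 1 | Only if the catch-all applies |
| Bilirubin | 0.8 to 1.6 | 1 to 2 | normal to 2 | No; explicit withdrawal rule |

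**Amylase and lipase.** The readings part in one band: not above ULN at Baseline, then above ULN but not above 1.5 times ULN.

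**AST, ALT and bilirubin.** Their own bullet withdraws drug above 3 times ULN (AST, ALT) or 1.5 times ULN (bilirubin). These are the lower ends of Grade 2 and do not use Grade 1. Smaller rises matter only if the catch-all also covers parameters that already have a bullet, and the text does not say.

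**Creatinine.** Its hold is set at 1.5 times Baseline and its withdrawal at 3 times Baseline, so neither uses Grade 1. Its Table 3 row begins above Baseline or above ULN and does not show the less-than form. What the SAP considers wrong in that row cannot be told from the documents.

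**Neutrophils and platelets.** Their hold rule does use Grade 1, but the SAP does not call those two definitions wrong.

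**The case against.** A reader might infer that safety decisions in general rest on limits the sponsor knows to be wrong, for all six parameters, and that sites are still acting on them. The documents do not support that. Apart from the amylase/lipase hold, the rules written specifically for these parameters use explicit multiples above Grade 1. That sites use the printed limits is inferred from the protocol text. The Laboratory Manual, the Manual of Procedures and any site letters are not available, and a SAP section on changes to analyses is not where a site instruction would be issued.

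Three further points carry weight. First, section 6.5.4 speaks of a change from normal to Grade 1 for blood counts, and section 7.4.1.1 refers investigators to CTCAE version 4.03 for adverse event severity. Many would therefore take the less-than sign as a misprint. Second, the SAP does not say that this sign is the error, and creatinine is on its list without showing it. Third, site actions and reported grades can disagree anyway: sites may act on local results with local ranges, while only central results are analysed. Correcting Table 3 would not remove that source of disagreement.

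These points narrow the concern. They do not dispose of it, because neither document corrects the site instruction, and one hold rule depends on an entry that the sponsor says is wrong. If some sites read the sign literally and others as a misprint, they will act differently on the same value.

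**Conclusion.** Table 3, protocol section 6.5.4 and SAP section 9 are inconsistent and must be reconciled. The clear effect is confined to one rule and one band: amylase or lipase moving from normal to above ULN but not above 1.5 times ULN. There the printed table gives no hold, and a Grade 1 starting above ULN would give one. A similar effect for AST, ALT (up to 3 times ULN) and bilirubin (up to 1.5 times ULN) is possible, depending on what the catch-all covers. The explicit withdrawal multiples and the creatinine hold do not change.

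This takes the printed less-than sign at face value, which fits the SAP's statement about the same entries, and uses an assumed lower limit for the comparison. The number of subjects or holds in the band is not in the documents, so the effect on the data cannot be sized.

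**What to change.** Bring Table 3, section 6.5.4 and SAP section 9 to one grading source through a protocol clarification or a letter to sites. In the same text, state whether the catch-all covers parameters that have their own bullet. In the clinical trial report, state which grading governed holds triggered at Grade 1; if dosing has already ended, this is the part that still helps. If a correction has already reached sites by another route, cite it in SAP section 9. No clinical limit is proposed here; that choice is the sponsor's. The cost is a short clarification to sites and a few sentences in the report, with no change to sample size, endpoints or the primary analysis.

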10.1 Definition of Protocol Deviations and Analysis Sets

No per Protocol analysis is planned.

Important protocol deviations are protocol deviations that might significantly affect the completeness, accuracy, and/or reliability of the study data or that might significantly affect a subject's rights, safety, or well-being.

The following important deviations will be identified and confirmed prior to or at the Data Review Meeting, which will occur before the database lock. The outcome of the Data Review Meeting will document the important protocol deviations as well as the finalization of the analysis population in a memo.

- Subjects that are dosed on the study despite not satisfying the inclusion criteria
- Subjects that develop withdrawal criteria whilst on the study but are not withdrawn
- Subjects that receive the wrong treatment or an incorrect dose
- Subjects that receive an excluded concomitant medication
- Deviation from Good Clinical Practice

- Inclusion and exclusion criteria violations
- Other violations/events that may have a relevant influence on the pharmacokinetic/pharmacodynamic (PK/PD) analysis (eg, adverse events (AEs), vomiting, sample processing errors, inaccurate dosing, etc.)

Any important protocol deviations that lead to the exclusion of a subject from an analysis set will be considered clinically important (see [Section 10.2](#)).

All important protocol deviations should be documented in Clinical Data Interchange Standards Consortium Study Data Tabulation Model (SDTM) (or Analysis Data Model (ADaM) for those derived by programming) whether identified through sites monitoring, medical review and/or programming based on the inclusion/exclusion criteria presented in the protocol. Important protocol deviations to be identified by programming as well as all clinically important protocol deviations are listed and described in [Appendix 3](#).

10.2 Definition of Analysis Sets and Subgroups

Screening Analysis Set (SCR)

The SCR includes all subjects who signed the informed consent.

Safety Analysis Set (SAF)

The SAF will include all subjects who received at least 1 dose of M2951 or placebo. The SAF will be used for all demographic/baseline characteristics and safety analyses.

Analyses performed on the SAF will consider subjects as treated. Subjects will be allocated to active arm if at least one dose of M2951 was taken during first 12-week treatment period.

The OLE SAF will include all subjects who received at least 1 dose of M2951 during the OLE period. The OLE SAF will be used for all safety analyses at the time of the final analysis.

mITT Analysis Set

The mITT Analysis Set will include all subjects who received at least 1 dose of M2951 or placebo and have at least 1 available ACR20 evaluation at a time point postdose. The mITT Analysis Set will be used for the analysis of all efficacy endpoints. Subjects will be analyzed as randomized.

The OLE mITT Analysis Set will include all subjects who received at least 1 dose of M2951 during OLE period and have at least 1 available efficacy evaluation (ACR components, ESR, anti-CCP, RF) at a time point after first dose in OLE period. The OLE mITT Analysis Set will be used for the analysis of efficacy endpoints at the time of the final analysis.

Pharmacokinetic Analysis Set

The PK Analysis Set will include all subjects who receive at least 1 dose of M2951 and have at least 1 quantifiable M2951 plasma concentration at a scheduled PK time point postdose without any important deviations or events that may impact the quality of the data or alter the evaluation of the PK. The PK Analysis Set will be used for all PK analyses. Subjects who receive placebo will not be included.

Pharmacodynamic Analysis Set

The PD Analysis Set will include all subjects who receive at least 1 dose of M2951 or placebo and have at least 1 measured PD endpoint, not including CCI [REDACTED], at a scheduled PD time point after first dose without deviations or important events affecting PD, and who provide evaluable PD data. All PD analyses, not including CCI [REDACTED], will be based on this analysis set.

Deviations, or changes to the procedures or events that may have a relevant influence on the PK may also influence PD analysis or impact the quality of the PD data and may lead to exclusion from the PD Analysis Set. Please see examples of deviations or events listed in Section 12.2.2.

In the case subjects or data are excluded from the PD analysis set, their PD data will be listed in the CSR and flagged.

The OLE PD Analysis Set will include all subjects who receive at least 1 dose of M2951 during OLE period and have at least 1 available PD endpoint at a time point after first dose in OLE period. All PD analyses, not including CCI [REDACTED], will be based on this OLE PD Analysis Set at time of final analysis.

CCI [REDACTED]
[REDACTED]
[REDACTED]
[REDACTED]
[REDACTED]
[REDACTED]
[REDACTED]
[REDACTED]
[REDACTED]

CCI [REDACTED]
[REDACTED] ■ [REDACTED]
[REDACTED]

Randomized Analysis Set

The randomized analysis set will include all randomized subjects. This set will be used to provide a listing for checking whether randomization occurred as planned.

The “as-treated” principle will be applied to all evaluations, except those based on the mITT Analysis Set, ie, subjects who receive a treatment other than the one assigned by randomization will be analyzed by the actual treatment received. The use of the analysis sets in the different analyses is summarized in the following table:

Table 1: Summary of analyses by sets

Analyses	SCR	SAF	OLE SAF	mITT Analysis Set	OLE mITT Analysis Set	PK Analysis Set	PD Analysis Set	OLE PD Analysis Set	CCI	Randomized Analysis Set
Subject Disposition status	✓									
Analysis sets	✓									
Subject disposition by visit										✓
Important Protocol Deviations										✓
Demographic and Baseline Assessments		✓								
Prior Medications		✓								
Concomitant Medications		✓	✓							
Concurrent procedures		✓	✓							
Compliance and Exposure		✓	✓							
Safety Analysis		✓	✓							
Primary Efficacy Analysis				✓						
Secondary Efficacy Analysis				✓						
OLE Efficacy Analysis					✓					
PK Analysis						✓				
PD Analysis							✓	✓		
CCI										
Randomization listing										✓

Subgroup analysis:

Subgroup analyses will be performed on randomized subjects with either:

- hsCRP at screening ≥ 3.6 mg/L
- hsCRP at baseline ≥ 3.6 mg/L

- hsCRP at screening ≥ 5 mg/L
- hsCRP at baseline ≥ 5 mg/L

Details of these subgroup analyses can be found in Table 14 of Section 16.

11 General Specifications for Statistical Analyses

All statistical analyses will be performed by PPD.

Treatment groups and IMP:

Treatment groups are defined as placebo + MTX and M2951 + MTX groups, except for the analyses including both the first 12-week treatment period and OLE period data, which will be summarized according to treatment groups 'Placebo/M2951 + MTX' and 'M2951 + MTX'. Unless otherwise indicated, all analyses will be presented separately for the two treatment groups. The IMPs are placebo and M2951.

Presentation of Tables/Figures

For the primary analysis at the end of first 12-week treatment period, drug code will be broken and tables and figures will be produced using true treatment groups and their true labels (ie, 'Placebo', 'M2951 50 mg BID'). For the final analysis, tables and figures will be produced using true treatment groups and the following labels: 'Placebo/M2951 50 mg BID' and 'M2951 50 mg BID/M2951 50 mg BID'.

Tables and figures will be sorted by treatment group (in order of 'Placebo' and 'M2951 50 mg BID', or 'Placebo/M2951 50 mg BID' and 'M2951 50 mg BID/M2951 50 mg BID' for final analysis) and chronological scheduled time point (where applicable).

Presentation of Listings:

All data recorded during the trial will be presented in individual data listings. All listings are sorted by treatment group (in order of 'Placebo' and 'M2951 50 mg BID', or 'Placebo/M2951 50 mg BID' and 'M2951 50 mg BID/M2951 50 mg BID' for final analysis), subject, and scheduled time point (where applicable), if not otherwise stated.

Data handling for the planned analysis:

For the primary analysis, data will be handled as follows:

- Data from OLE, or safety follow-up posterior to OLE, will be excluded from the primary analysis. This exclusion will be performed at the ADaM level; no selection will be performed, neither at the data management level, nor at the SDTM level.
- As the database lock for the primary analysis will be based on data up to and including the last patient's last dose of IMP (LPLD) during 12-Week treatment period, all data from screening to LPLD during the 12-Week treatment period for all subjects will be locked and available in the database for the primary analysis.
- A cut-off date will be applied at the SDTM level: all data posterior to LPLD during 12-Week treatment period will be removed from the database. Details on the implementation of this cut-off date are available in the document named *SDTM Cut-off date implementation rules_BTKi(M2951)-Compound_v2.0.docx*
- For all subjects, data during the 12-week treatment period up to and including the LPLD will be included for the primary analysis except for the safety follow-up data. All safety follow-up data will be reported for the mITT population at the final analysis stage.
- Data selection for the primary and final analyses will be identified at the ADaM level first before any statistical calculations can start. Therefore, the data handlings described in all tables in the following sections of this SAP will depend on data selected in the ADaM level.

For the final analysis, data will be presented on subjects who agreed to participate in OLE.

Presentation of continuous and qualitative variables:

Continuous variables will be summarized using descriptive statistics, ie

- number of subjects (N)
- number and percentage of non-missing values
- number and percentage of missing values
- mean, standard deviation (SD)
- median, 25th Percentile - 75th Percentile (Q1-Q3)
- minimum and maximum

For both continuous and qualitative variables, percentages such as 0% or 100% should be reported with the same format used for the column, together with the count of observations. For example, if the count of observations is zero, then display '0 (0.0)'; if the count of observations represents 100%, then display 'xx (100.0)'.

Qualitative variables will be summarized by counts and percentages. Unless otherwise stated, the calculation of proportions will be based on the number of subjects in the analysis set of interest. Therefore counts of missing observations will be included in the denominator and presented as a separate category.

In case the analysis refers only to certain visits, percentages will be based on the number of subjects in the analysis set of interest, unless otherwise specified. Total of missing and non-missing observations at each time-point will reflect the population still in the trial at that time. For example, if a subject is still in the trial at the time-point but with missing data, it should be counted in the number of missing observations.

Pharmacodynamic endpoints will be reported as described above for presentation of continuous and qualitative variables.

Specific rules for PK concentrations and PK parameters

Plasma concentrations of M2951 will be presented descriptively by study day and nominal time point for the PK analysis set including number of subjects (N), number of observations (n), mean, SD, coefficient of variation (CV%) median, minimum, and maximum. The below limit of quantification (BLQ) PK concentration values will be set to zero prior to computing descriptive statistics of PK concentrations. Missing concentrations will be omitted from the calculation of descriptive statistics.

Individual plasma and mean concentration-time plots will be provided using a linear and semi-logarithmic scale.

Descriptive statistics for PK parameters (see Section 16.3.2 for calculations) will be summarized by study day (N, n, arithmetic mean, SD of the arithmetic mean, CV%, median, minimum, maximum geometric mean [GeoMean], geometric coefficient of variation [GeoCV%], and the 95% CI for the GeoMean). For t_{max} , only n, minimum, median, and maximum will be reported. For calculation and presentation of PK descriptive statistics, and the inferential statistical analysis, values as presented in the data listings will be used as the source data. Minimum, maximum, mean, GeoMean, median, Q1, Q3, and 95% CI for mean or GeoMean will be presented to the same significant figure precision as listed data. Standard deviation will be presented to 1 significant figure more than the precision of the data listed. The CV% and GeoCV% will always be reported to 1 decimal place. Derived parameters will be reported to 3 significant figures, except for parameters that are taken directly from concentration data which will be reported using similar precision to those from which they were derived or elapsed sampling times which will be reported as 2 decimal places.

Definition of baseline:

For the purpose of statistical analysis, baseline is defined as the last non-missing measurement prior to the first dose of study drug as described in the following table:

Table 2: Definition of baseline

Randomized	Time Period	Baseline
Placebo+MTX	First 12-week treatment period	Last non-missing measurement prior to first dose of study drug of the 12-week treatment period
	OLE Period	Last non-missing measurement prior to the first dose of M2951 of the OLE period
M2951+MTX	First 12-week treatment period	Last non-missing measurement prior to first dose of study drug of the 12-week treatment period
	OLE Period	Last non-missing measurement prior to first dose of study drug of the 12-week treatment period

Definition of CFB:

CFB and percent CFB will be computed as follows:

- CFB = visit value – baseline value
- Percent CFB = 100 * (visit value – baseline value) / baseline value

Definition of duration:

Unless otherwise specified, duration will be calculated as the difference between start and stop date + 1 (e.g. duration of AE (days) = AE start date – AE stop date + 1). Unless otherwise specified, missing dates will not be imputed.

The time since an event will be calculated as:

- date of event minus reference date +1 (eg days in study at onset of AE = AE start date - date of randomization + 1) if date of event is equal or greater than reference date
- date of event minus reference date (eg days in study at onset of AE = AE start date - date of randomization) otherwise

Conversion factors:

The following conversion factors will be used to convert days into months or years: 1 month = 30.4375 days, 1 year = 365.25 days. For time windows calculation, 1 month is expressed as 30 days.

Definition of Body Mass Index (BMI) (kg/m²):

BMI will be computed as weight / (height²), where weight is expressed in kg and height in m.

Handling of missing data:

The Table 3 summarizes how missing data will be handled for each ACR component and DAS28-hsCRP:

Table 3: Missing data handling of ACR and DAS28-hsCRP

Period covered	Parameter	Methods of imputation
12-Week treatment period	ACR	
 1. LOCF-NR (Primary analysis): 
 a. Imputation of each component using LOCF b. Derivation of ACR (responder/non-responder) c. If the subject discontinues from treatment, the subject will be considered as non-responder for all visits after discontinuation 2. Non-responder imputation (sensitivity analysis) 
 a. Derivation of ACR (responder/non-responder) using observed ACR components b. If the ACR is missing, then the ACR will be assigned as non-responder 3. Other sensitivity analysis (see Table 13)
	DAS28-hsCRP	LOCF: 
 a. Imputation on each component using LOCF b. Derivation of DAS28-hsCRP at each timepoint
OLE period	ACR	No imputation
	DAS28-hsCRP	No imputation

Unless otherwise specified, missing data will not be replaced.

In all subject data listings, imputed values will be presented. In all listings imputed information will be flagged. Non imputed partial dates will be presented in a format such as “____YYYY”. Where imputation is defined, an imputed date with flag (ie, D for day, M for month) will be reported.

Missing statistics, eg when they cannot be calculated, should be presented as ‘nd’ (denoting “not done”). For example, if n=1, the measure of variability (SD) cannot be computed and should be presented as ‘nd’.

In case of zero records, an empty output with 0 occurrences, or a sentence mentioning that there are no data, will be presented. For tables of AEs and Deaths (outputs required for EudraCT and/or clinicaltrial.gov), if there are no observations, the output must contain the first line ‘Subject with...’ or ‘Subject who died’ displayed with 0 occurrence.

If the System Organ Class (SOC) or Anatomical Therapeutic Class (ATC) term is missing/not coded yet, then 'Uncoded SOC' (or 'Uncoded ATC') will be indicated at the ADaM level. When a Preferred Term (PT) is missing, it will be set to 'Uncoded PT: verbatim text'.

Treatment day:

Treatment day is defined as relative day to the start date of treatment. Treatment day will be calculated accordingly, ie:

- For primary analysis, treatment day 1 is defined as the date of first administration of any IMP.
- For final analysis, treatment day 1 is defined as the first administration of M2951:
 - For subjects who switch from placebo to M2951, the treatment day 1 will be defined as the first administration of M2951 in OLE period
 - For subjects who have taken M2951 during 12-Week treatment period and continue with the same treatment during OLE, the treatment day 1 will be defined as the first administration of M2951 during 12-Week treatment period

The day before is defined as Treatment day -1 (no Treatment day 0 is defined).

Repeated and unscheduled measurements:

Data collected at unscheduled visits will be included and analyzed for safety analyses in the same fashion as the data collected at scheduled visits. Unscheduled measurements will also be used for shift tables.

Gap between 12-Week treatment period and OLE period

Subjects with a gap strictly greater than 4 weeks between 12-Week treatment period and OLE period will be analyzed the same way as subjects without a gap. Specific data listings on safety data (AEs and all laboratory data) will be produced for these subjects for the final analysis.

Time windows

As a measurement may have been performed out of window, data will be re-allocated according to time windows defined in Table 4, so that each measurement is allocated to the closest timepoint. In case of a gap between 12-Week treatment period and OLE, time windows allocation will be handled case by case at the time of statistical analysis.

For efficacy and safety analyses, each measurement will be assigned an analysis visit number first according to Table 4. The analysis visit will then be used for all missing data imputations, analysis variable derivations, statistical calculations and presentations. For patient data listings by timepoint, the visit as collected in the database as well as the analysis visit will be displayed.

Table 4: Time windows

Analysis	Treatment groups	Period covered	Interval (days) [Date of assessment – Date of first dose + 1]	Analysis Visit	
Primary analysis	Placebo or M2951 50 mg BID	12-Week treatment period	1	Day 1	
			[2 ; 11)	Week 1 – Day 7	
			[11 ; 21)	Week 2 – Day 14	
			[21 ; 35)	Week 4 – Day 28	
			[35 ; 49)	Week 6 – Day 42	
			[49 ; 70)	Week 8 – Day 56	
			[70 ; 91)	Week 12 – Day 84	
Final analysis	Placebo/M2951 50 mg BID	12-Week treatment period	NA	NA	
			OLE period	1	D1 – OLE
				[2 ; 22)	D14 – OLE
				[22 ; 60)	Month 1 – OLE
				[60 ; 135)	Month 3 – OLE
	[135 ; 187)	Month 6 – OLE			
	M2951 50 mg BID/ M2951 50 mg BID	12-Week treatment period	1	Day 1	
			[2 ; 11)	Week 1 – Day 7	
			[11 ; 21)	Week 2 – Day 14	
			[21 ; 35)	Week 4 – Day 28	
			[35 ; 49)	Week 6 – Day 42	
			[49 ; 70)	Week 8 – Day 56	
			[70 ; 91)	Week 12 – Day 84	
			OLE period	[70 ; 91)	D1 – OLE
[91 ; 106)				D14 – OLE	
[106 ; 144)	Month 1 – OLE				
[144 ; 219)	Month 3 – OLE				
		[219 ; 271)	Month 6 – OLE		

Software:

Non-compartmental computation of PK parameters will be performed using Phoenix® WinNonlin® Version 6.4, or higher (PPD [redacted]). Graphics may be prepared with SAS Version 9.4, or higher; SigmaPlot® 12.5, or higher (PPD [redacted]); or Phoenix WinNonlin 6.4, or higher.

All other statistical analyses will be performed using SAS® (PPD [redacted]).

12 Trial Subjects

The subsections in this section include specifications for reporting subject disposition and treatment/trial discontinuations. Additionally procedures for reporting protocol deviations are provided.

